7.4 Treatment Compliance

Treatment compliance (number of days when the subject actually received the IMP/number of days for which the IMP was prescribed) will be grouped into < 70%, ≥ 70% to < 80%, ≥ 80% to < 90%, and ≥ 90%, and its frequency distribution will be determined in the efficacy analysis set.

7.5 Prior and Concomitant Medications

Numbers and proportions of subjects who used medications before, during, and after the treatment period will be determined by drug class and preferred term of the World Health Organization Drug Dictionary (WHODD) version Global B3 March 2018 in the safety analysis set.

Similar summarization will be performed for antipsychotics.

7.6 Protocol Deviations

Numbers and proportions of subjects with major deviations from the protocol will be determined for each category (treatment-related deviations, eligibility-related deviations, a failure to discontinue the trial when the subject meets the withdrawal criteria, procedure-related deviations that affect evaluation of the primary endpoint, use of prohibited medications, and overall) and each trial site, in the safety analysis set.

8 Efficacy Analysis

Efficacy analysis will be performed using the efficacy analysis set. Baseline is defined as the last data obtained prior to initiation of IMP treatment in the trial.

- MADRS total score
- CGI-S
- CGI-I
- HAM-D 17 total score
- Mean SDS score and score for each item

Descriptive statistics of actual measurements and changes from baseline at each time point and the last assessment time point (Week 52 LOCF) will be determined.

- MADRS response rate (proportion of subjects in whom MADRS total scores have been reduced by at least 50% from baseline)
- MADRS remission rate (proportion of subjects in whom MADRS total scores have been reduced by at least 50% from baseline, with their resultant MADRS total scores being ≤ 10)
- CGI-I improvement rate (proportion of subjects who score 1 or 2 on the CGI-I scale)
Numbers and proportions of subjects will be determined at each time point and the last assessment time point (Week 52 LOCF).

8.1 Subgroup Analyses

No subgroup efficacy analyses will be performed.

9 Other Analyses

Other analyses will be performed using the efficacy analysis set. Baseline is defined as the last data obtained prior to initiation of IMP treatment in the trial.

- EuroQol-5 Dimension, 5 response level version (EQ-5D-5L)
For each item, descriptive statistics of actual measurements and changes from baseline at each time point and the last assessment time point (Week 52 LOCF) will be determined.

10 Safety Analyses

Safety analysis will be performed using the safety analysis set. Baseline is defined as the last data obtained prior to initiation of IMP treatment in the trial.

10.1 Extent of Exposure

Frequency distribution of the duration (days) of treatment with the IMP (1-7, 8-14, 15-28, 29-56, 57-84, 85-112, 113-140, 141-168, 169-196, 197-224, 225-252, 253-280, 281-308, 309-336, 337-364, > 364) will be determined. Similar summarization will be performed for each requisite concomitant medication subgroup.

Frequency distribution of the duration (days) of treatment with a requisite concomitant medication (1-7, 8-14, 15-28, 29-56, 57-84, 85-112, 113-140, 141-168, 169-196, 197-224, 225-252, 253-280, 281-308, 309-336, 337-364, > 364) will be determined.

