### **3.7.1.3 Observations/Examinations in the Treatment Period (52 Weeks)**

The investigator or subinvestigator will judge eligibility of rollover subjects from the double-blind trial (331-102-00058), based on the results of examinations and assessments at baseline and clinical laboratory values and 12-lead ECG at Week 6 of the double-blind period (Phase B) of the double-blind trial (331-102-00058). The treatment period will commence within 28 days from Week 6 of the double-blind period (Phase B) of the double-blind trial (331-102-00058). If the examinations and assessments at Week 6 of the double-blind period (Phase B) of the double-blind trial (331-102-00058) have been performed within a period of 7 days prior to the day of baseline assessment (Day –7 to Day 0), the data will be used as baseline data for this trial. The eligibility of new subjects will be judged based on the results of examinations and assessments at screening and baseline. The result of the eligibility judgement will be registered in the IWRS and

recorded in the source documents and CRF. If subjects are judged to be eligible, the date of enrollment in the treatment period will be recorded in the source documents and CRF.

Eligible subjects will start receiving brexpiprazole at a starting dose of 1 mg/day, in an open-label manner.

The investigator or subinvestigator will perform examinations/assessments in the treatment period, as specified in the schedule of examinations/assessments (Table 3.7-1) and record the result along with the visit date in the source documents and the CRF.

The investigator or subinvestigator will register the required items in IWRS at the time of each subject's completion of IMP administration in Week 52.

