#### **3.7.1.6 Acceptable Window for Testing**

Observations/examinations and other procedures are to be performed within an acceptable window for testing, as specified in Table 3.7.1.6-1, with consideration of the availability of each subject for site visits, etc.

Examination Point	Reference Day	Acceptable Window (From the Reference Day)
At screening (new subjects only)	Day of baseline assessment	-28 to -1 days
Day of baseline assessment	Day 1	-
Week 1 of the treatment period	Day 8	± 2 days
Week 2 of the treatment period	Day 15	± 2 days
Week 4 of the treatment period	Day 29	± 2 days
Week 8 of the treatment period	Day 57	± 7 days
Week 12 of the treatment period	Day 85	± 7 days
Week 16 of the treatment period	Day 113	± 7 days
Week 20 of the treatment period	Day 141	± 7 days
Week 24 of the treatment period	Day 169	± 7 days
Week 28 of the treatment period	Day 197	± 7 days
Week 32 of the treatment period	Day 225	± 7 days
Week 36 of the treatment period	Day 253	± 7 days
Week 40 of the treatment period	Day 281	± 7 days
Week 44 of the treatment period	Day 309	± 7 days
Week 48 of the treatment period	Day 337	± 7 days
Week 52 of the treatment period	Day 365	± 7 days
At discontinuation	-	-

At discontinuation: Performed within a possible window at a feasible time point.

The starting point of the post-treatment observation period is the day of the final IMP administration.

Period	Reference Day	Acceptable Window (From the Reference Day)
Day of the final IMP administration	Day 1	-
The post-treatment observation period	Day 31	± 5 days

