#### (3) Compliance instruction

The investigator, subinvestigator, or IMP manager will provide subjects with compliance instructions with particular attention to the following points:

- The subject should take the IMP once daily, removing only the prescribed daily amount of the IMP from the sheet.
- The subject must bring any missed/unused doses (IMP tablets) to the trial site at the next visit.
- Contact information for any questions about taking the IMP
- The subject must not discard any empty IMP sheets but should bring them to the trial site at the next visit.
- The subject should be withdrawn from the trial if the subject's IMP compliance during an interval between 2 consecutive scheduled visits is less than 65%.

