### **3.8.3.3 Withdrawal of Consent**

All subjects have the right to withdraw their consent from further participation in the trial at any time without prejudice. Subjects cannot withdraw consent for use of data already collected as part of the trial, but only for future participation. The investigator or subinvestigator can also discontinue a subject's participation in the trial at any time if medically necessary. Unless the subject provides their written withdrawal of consent or there is other written documentation by the investigator or subinvestigator confirming the subject's verbal intent to completely withdraw from the trial, subjects should be followed for all protocol-specified evaluations and assessments, if possible.

Complete withdrawal of consent requires refusal by a subject of ALL of the following methods of follow up (these methods of follow up will also be noted in the trial ICF):

- Participation in all follow-up procedures specified in the protocol (whether in-clinic, by telephone, or by an in-home visit).
- Participation in a subset of protocol specified follow-up procedures (by a frequency schedule and method, as agreed by subject and staff).
- Contact of the subject by trial personnel, even if only by telephone, to assess current medical condition, and obtain necessary medical or laboratory reports relevant to the trial's objectives.
- Contact of alternative person(s) who have been designated in source documents as being available to discuss the subject's medical condition, even if only by telephone, mail, or e-mail (eg, family, spouse, partner, legal representative, friend, neighbor, or physician).
- Access to medical information from alternative sources (eg, hospital/clinic medical records, referring doctor's notes, public records, dialysis, transplantation or vital registries, social media sources).

Withdrawal of consent is a critical trial event and therefore should be approached with the same degree of importance and care as is used in initially obtaining informed consent. The reasons of a subject for an intended withdrawal need to be completely understood, documented, and managed to protect the rights of the subject and the integrity of the trial. A subject may initially express their desire to discontinue IMP administration, which is not equivalent to a complete withdrawal of consent for further participation (see [Section](#)

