### **3.10 Definition of Completed Subjects**

The treatment period is defined as the time period during which subjects are evaluated for safety and efficacy irrespective of whether the subject actually received all doses of the IMP. Subjects who are evaluated at the last scheduled visit during the treatment period will be defined as trial completers. For the purposes of this trial, subjects who are evaluated at Week 52 of the treatment period will be defined as trial completers.

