### **7.1 Sample Size**

To verify the safety of long-term administration, the target number of subjects to complete 52 weeks of administration was set at around 100 subjects. Due to the availability of data on safety in elderly subjects from foreign clinical trials, the sample size needed to assess the safety of brexpiprazole in the elderly was set as 30 new subjects (elderly subjects of age 65 and above) receiving IMP administration.

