3.4 Trial Visit Window

For all endpoints, acceptable windows for analysis are specified, and analysis should be based on the analysis time points regardless of time points recorded on the case report form.

Acceptable windows for analysis are shown in Table 3.4-1. Day 1 is defined as the day when treatment with the investigational medicinal product (IMP) begins. If multiple data exist within an acceptable window, the last data within the window will be used in analysis. Data obtained 7 days or later after the final dosing will be excluded from the analysis.

Table 3.4-1	Acceptable Windows for Analysis	
Week	Target Day	Trial Day Interval
Baseline	1	- 1
Week 1	7	2 - 10
Week 2	14	11 - 21
Week 4	28	22 - 42
Week 8	56	43 - 70
Week 12	84	71 - 98
Week 16	112	99 - 126
Week 20	140	127 - 154
Week 24	168	155 - 182
Week 28	196	183 - 210
Week 32	224	211 - 238
Week 36	252	239 - 266
Week 40	280	267 - 294
Week 44	308	295 - 322
Week 48	336	323 - 350
Week 52	364	351 - 385

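### Does the exposure table need a new cut at 364 days so that subjects completing 52 weeks of dosing can be counted against the target of about 100?

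*SAP*

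**What the plan says.** Protocol 7.1 and SAP 4 give the main target in the same words: "the target number of subjects to complete 52 weeks of administration was set at around 100 subjects". Neither attaches a rate, precision, test or dropout allowance to it, and SAP 6 plans no primary or secondary outcome variables.

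SAP 10.1 plans a frequency distribution of days on study drug whose last rows are given as "281-308, 309-336, 337-364, > 364) will be determined". It is reported in CT-7.1. No formula for that duration is printed, although SAP 7.3 and 7.4 do give formulas for disease duration and for compliance. SAP 3.4 fixes the origin: "Day 1 is defined as the day when treatment with the investigational medicinal product (IMP) begins".

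Protocol 3.10 supplies the only definition of completion: "subjects who are evaluated at Week 52 of the treatment period will be defined as trial completers". It says that this does not depend on every dose having been taken. Protocol 3.7.1.3 nevertheless ties the two ideas together by asking sites to register "each subject's completion of IMP administration in Week 52". The completer count appears in CT-1.1, and CT-2.3 breaks completion down by the same day periods (SAP 7.1). Protocol 3.7.1.6 places "Week 52 of the treatment period" at Day 365, plus or minus 7 days. SAP Table 3.4-1 uses a target of Day 364 and a window of Days 351 to 385.

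**The concern.** The target is worded in terms of dosing, and the 52-week duration is itself justified by a notification on long-term population exposure. The natural place to check the target is therefore the exposure table. There the boundary falls on the wrong side: exactly 52 weeks lands in the 337-364 row, and the top row starts at 365 days. The nominal Week 52 visit sits on that boundary, so a one-day difference in last dose moves a subject between rows.

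Completion is defined by attendance, not by dosing. Protocol 3.8.3.3 says that, short of complete withdrawal of consent, "subjects should be followed for all protocol-specified evaluations and assessments, if possible", so a subject who stopped the drug might still be evaluated at Week 52. The SAP does not say which count answers the target. What would be at stake is how long-term exposure is reported: a reader who looked only at the top row could think the trial fell short when it had not.

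**Working it through.** The figure of about 100 has no statistical inputs, so there is no sample-size calculation to reproduce. The check is where the days fall.

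**1. Position of 52 weeks.** 52 × 7 = 364, the upper end of the 337-364 row. 48 × 7 = 336, so that row runs from 48 weeks plus 1 day to 52 weeks. From CT-7.1 alone, the number with at least 52 weeks lies between the count in the > 364 row and the sum of the last two rows.

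**2. On-protocol completers.** Day 365 ± 7 gives 15 possible visit days, 358 to 372. Take duration = last dose day − first dose day + 1.

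| Last dose | Durations | In 337-364 | > 364 | ≥ 364 | ≥ 357 |
|---|---|---|---|---|---|
| on the visit day | 358-372 | 7 | 8 | 9 | 15 |
| the day before | 357-371 | 8 | 7 | 8 | 15 |

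The documents do not give actual visit timing. Assuming 100 completers spread evenly over the window, the > 364 row shows 100 × 8/15 ≈ 53 or 100 × 7/15 ≈ 47. In the extreme case of every visit on Day 365, durations are 365 or 364 and the row shows 100 or 0.

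**3. Does the missing formula cause this?** No. The lowest row starts at 1 day and Day 1 is the first dosing day. A subject with one dose has last − first = 0, which no row holds; adding 1 gives 1, which does. Inclusive counting is therefore implied. Both lines of the table use that same formula. They differ only in the date of the last dose, which is recorded for each subject (Protocol 3.7.6 (1)). Printing the formula would leave the figures in step 2 unchanged.

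**4. Would a new cut help?** With the same even spread, a row for at least 364 days would show 100 × 9/15 = 60 or 100 × 8/15 ≈ 53. If every visit fell on the SAP's own target, Day 364, durations would be 364 or 363 and the new row would show 100 or 0: the same edge, one day earlier. A row for at least 357 days holds all 15 visit days in both cases, but 357/7 = 51 weeks. It does not count 52 weeks of dosing and, for on-protocol completers, repeats CT-1.1.

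**5. How far can the completer count drift from dosing?** Protocol 3.7.6 (3) calls for withdrawal if "IMP compliance during an interval between 2 consecutive scheduled visits is less than 65" per cent. Assume that prescribed days equal days between visits and that doses are taken from the Week 48 visit day without gaps. Then

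earliest last dose = Week 48 day + ceil(0.65 × (Week 52 day − Week 48 day)) − 1.

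- Nominal visits, Days 337 and 365: 0.65 × 28 = 18.2, so 19 tablets, and 337 + 19 − 1 = Day 355.
- Smallest value over the allowed windows (Days 330-344 and 358-372): for example 330 to 358, again 19 tablets, and 330 + 19 − 1 = Day 348.

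Day 348 is 364 − 348 = 16 days short of 52 weeks and still lies in the 337-364 row. A completer who meets the 65% rule with visits in window is therefore always in one of the last two rows.

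**The case for a change.** The best case for a change is that exposure is a headline result in an uncontrolled safety trial, that the target is worded as administration while completion is defined by evaluation, and that the SAP takes care to define other durations but not this one. CT-2.3 does not settle the matter, because it uses the same day cut-offs. A line of definition and a cumulative row would cost almost nothing and would fix the rule before the counts are seen.

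Part of this stands. CT-7.1 alone does only bracket the number, and the SAP does not name the table that answers the target. A cumulative row for at least 364 days beside the completer count would be harmless. But it would read below the completer count for subjects whose Week 52 visit was on Days 358 to 363, which is on protocol, so it would need its own explanation. The existing rows are whole-week periods shared with the adverse-event onset table (SAP 10.2) and the antidepressant exposure table (SAP 10.1), which is a sensible reason to keep them. The worry about choosing a rule after seeing the counts is slight, since the rows already imply inclusive counting and the last dose date is recorded.

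**Conclusion.** No change to the plan is needed. The observation is correct as a point of table layout: exactly 364 days is grouped with stops from Day 337, and no duration formula is printed. Followed as written, the plan still answers an approximate target. CT-1.1 counts completers under the only definition given, the protocol links that visit to the end of dosing, and the 65% rule keeps the last dose of an on-protocol completer at Day 348 or later. An analyst who wants the exact number with 52 weeks of dosing can derive it from the recorded dosing dates, which also appear in listing SMED-1.1.

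Under an even spread of visits, moving the cut would shift the top row from about 53 to 60 per 100 completers, or from about 47 to 53, and would not remove the edge. These figures rest on the assumed visit spread, and the Day 348 bound on the assumptions in step 5. A subject who stopped the drug but attended Week 52 remains possible, though the compliance rule should make that uncommon. The second target, 30 new elderly subjects receiving the drug, does not depend on the 364-day cut. No test, error rate or conclusion changes.

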10.2 Adverse Events

All adverse events (AEs) will be coded by Medical Dictionary for Regulatory Activities (MedDRA) (Ver. 24.0) System Organ Class (SOC) and Preferred Term (PT). Numbers and proportions of subjects with the following AEs will be summarized by SOC and PT. If an AE occurs more than once in the same subject, the severest event will be used in summarization.

- Adverse events occurring after initiation of IMP administration (treatment-emergent adverse events [TEAEs])
- TEAEs by severity
- TEAEs with an outcome of death
- Serious TEAEs
- TEAEs leading to discontinuation of the IMP
- TEAEs occurring in $\geq 2\%$ of subjects in any group
- TEAEs by date of initial onset (1-7, 8-14, 15-28, 29-56, 57-84, 85-112, 113-140, 141-168, 169-196, 197-224, 225-252, 253-280, 281-308, 309-336, 337-364, > 364 , post-trial treatment)

TEAEs potentially causally related to the IMP will also be summarized in the same manner.

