- Pregnancies are also defined as IREs. Although normal pregnancy is not an AE, it will mandate IMP discontinuation and must be reported on an IRE form to the sponsor. Pregnancy will only be recorded in the source documents and the AE Section of the CRF if there is an abnormality or complication. This applies both to pregnancies of subjects and pregnancies of subjects' partners.

Clinical Laboratory Assessment Value Changes: It is the investigator's or subinvestigator's responsibility to review the results of all laboratory tests as they become available. This review will be documented by the investigator's or subinvestigator's dated signature on the laboratory report. For each abnormal laboratory test result, the investigator or subinvestigator needs to verify whether this is an abnormal (ie, clinically relevant) change from baseline for that individual subject. This determination, however, does not necessarily need to be made the first time an abnormal value is observed. The investigator or subinvestigator may repeat the laboratory test or request additional tests to verify the results of the original laboratory tests. If this laboratory value is considered medically relevant by the investigator or subinvestigator (subject is symptomatic, requiring corrective treatment or further evaluation), or if the laboratory value leads to discontinuation or meets the criteria for an SAE, this is considered an AE.

Severity: Adverse events will be graded on a 3-point scale and reported. The intensity of an AE is defined as follows:

**1 = Mild:** Discomfort noticed, but no disruption to daily activity.

**2 = Moderate:** Discomfort sufficient to reduce or affect normal daily activity.

**3 = Severe:** Inability to work or perform normal daily activity.

IMP Causality: Assessment of causal relationship between an AE and the IMP:

**Related:** There is a reasonable possibility of a temporal and causal relationship between the IMP and the AE.

**Not related:** There is no temporal or reasonable relationship between the IMP and the AE.

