## 5.2 Eliciting and Reporting Adverse Events

The investigator or subinvestigator will periodically assess subjects for the occurrence of AEs. To avoid bias in eliciting AEs, subjects should be asked the nonleading question: “How have you felt since your last visit?” For all AEs (serious and nonserious) reported by the subject, the event name, start and stop dates, severity, seriousness, relationship to IMP, actions taken regarding IMP administration, and outcome thereof must be recorded in the source documents and CRFs provided by the sponsor. Adverse event and SAE collection is to begin after a subject has signed the ICF.

Use medical terminology in AE reporting. Adverse events should be reported as a single unifying diagnosis whenever possible or, in the absence of a unifying diagnosis, as individual signs or symptoms. Exacerbation or disease progression should be reported as an AE only if there are unusual or severe clinical features that were not present, or experienced earlier, or not expected based on the course of the condition. If a reported AE has worsened in severity or seriousness, it should be reported as a new AE on the CRF.

In addition, the sponsor must be notified immediately by e-mail, in principle, of any IREs according to the procedure outlined below, in [Section 5.3](#) Immediately Reportable Events. Special attention should be paid to recording hospitalization and concomitant medications.

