5.3 Handling of Missing Data

The analysis of last assessment time point will be performed using the last observation carried forward method (herein after referred to as "LOCF"), by which missing data at Week 52 will be imputed by the last observed data after initiation of IMP treatment.

6 Primary and Secondary Outcome Variables

Neither primary nor secondary outcome variables are planned.

7 Disposition and Demographic Analysis

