- CT-7.2 Extent of Exposure to ADT (Safety Analysis Set)
- CT-7.3 Summary of Treatment Compliance (Efficacy Analysis Set)
- CT-8.1 Adverse Events (All Causalities) (Safety Analysis Set)
- CT-8.2.1 Incidence of TEAEs by MedDRA System Organ Class and Preferred Term (Safety Analysis Set)
- CT-8.2.2 Incidence of Drug-related TEAEs by MedDRA System Organ Class and Preferred Term (Safety Analysis Set)
- CT-8.3.1 Incidence of TEAEs by MedDRA System Organ Class, Preferred Term and Severity (Safety Analysis Set)
- CT-8.3.2 Incidence of Drug-related TEAEs by MedDRA System Organ Class, Preferred Term and Severity (Safety Analysis Set)
- CT-8.4.1 Incidence of Deaths due to TEAEs by MedDRA System Organ Class and Preferred Term (Safety Analysis Set)
- CT-8.4.2 Incidence of Deaths due to Drug-related TEAEs by MedDRA System Organ Class and Preferred Term (Safety Analysis Set)
- CT-8.5.1 Incidence of Serious TEAEs by MedDRA System Organ Class and Preferred Term (Safety Analysis Set)
- CT-8.5.2 Incidence of Serious Drug-related TEAEs by MedDRA System Organ Class and Preferred Term (Safety Analysis Set)
- CT-8.6.1 Incidence of TEAEs Resulting in Discontinuation of IMP by MedDRA System Organ Class and Preferred Term (Safety Analysis Set)
- CT-8.6.2 Incidence of Drug-related TEAEs Resulting in Discontinuation From Study by MedDRA System Organ Class and Preferred Term (Safety Analysis Set)
- CT-8.7.1 Incidence of TEAEs of at Least 2% in Any Group by MedDRA System Organ Class and Preferred Term (Safety Analysis Set)
- CT-8.7.2 Incidence of Drug-related TEAEs of at Least 2% in Any Group by MedDRA System Organ Class and Preferred Term (Safety Analysis Set)
- CT-8.8.1 Incidence of TEAEs by MedDRA System Organ Class, Preferred Term and Time to First Onset (Safety Analysis Set)
- CT-8.8.2 Incidence of Drug-related TEAEs by MedDRA System Organ Class, Preferred Term and

	Time to First Onset (Safety Analysis Set)
CT-8.9.1	Incidence of TEAEs for EPS (Safety Analysis Set)
CT-8.9.2	Incidence of TEAEs for Neuroleptic Malignant Syndrome (Safety Analysis Set)
CT-8.9.3	Incidence of TEAEs for Rhabdomyolysis and CPK Elevation (Safety Analysis Set)
CT-8.9.4	Incidence of TEAEs for Seizures (Safety Analysis Set)
CT-8.9.5	Incidence of TEAEs for Orthostatic Hypotension, Dizziness, and Syncope (Safety Analysis Set)
CT-8.9.6	Incidence of TEAEs for Suicidality (Safety Analysis Set)
CT-8.9.7	Incidence of TEAEs for Somnolence (Safety Analysis Set)

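### SAP 10.2 applies its severest-event rule to every TEAE table, which contradicts the first-onset tables CT-8.8.1/8.8.2

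*SAP*

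**What the plan says.** SAP 10.2 sets the unit of summary: "Numbers and proportions of subjects with the following AEs will be summarized by SOC and PT". The next sentence is the rule for repeats: "If an AE occurs more than once in the same subject, the severest event will be used in summarization". The list of tables follows: all TEAEs, by severity, fatal, serious, leading to IMP discontinuation, occurring in at least 2% of any group, and "TEAEs by date of initial onset". After the list comes: "TEAEs potentially causally related to the IMP will also be summarized in the same manner". No table is exempted from the repeat rule.

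SAP Appendix 5 titles CT-8.8.1 "Incidence of TEAEs by MedDRA System Organ Class, Preferred Term and Time to First Onset", and CT-8.8.2 is its drug-related counterpart.

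Protocol 5.2 governs how repeat records arise: "If a reported AE has worsened in severity or seriousness, it should be reported as a new AE on the CRF". Protocol 5.1 gives the scale: "Adverse events will be graded on a 3-point scale and reported". Protocol 7.7.1, the protocol's own AE analysis section, has no severest-event rule and no onset table, so it does not settle which instruction governs.

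**The concern.** A rule that keeps the severest record is right for a severity table. A first-onset table needs a different selection, the earliest record. SAP 10.2 puts the first rule over the second table and does not say which prevails, so a programmer has to choose.

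The choice has a direction. Under Protocol 5.2 an AE that worsens in severity has its higher grade on a later record by construction. If the rule is applied as written, early-onset events that later worsen are tabulated as later-onset events.

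This matters because the trial assesses long-term safety descriptively. SAP Section 6 states: "Neither primary nor secondary outcome variables are planned". The onset table also has short early intervals, with a boundary between Days 7 and 8, close to the Week 1 step from 1 to 2 mg/day described in SAP 3.2. A mild event on Day 5 that becomes moderate on Day 10 would move from 1–7 to 8–14, which hides that it began on the starting dose.

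**Working it through.** The documents state no figure on this point, so there is nothing to reproduce. The check sets the rules side by side and works examples through the SAP's own intervals.

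**Inputs from the documents**
- Onset intervals (SAP 10.2): 1–7, 8–14, 15–28, then twelve 28-day intervals from 29–56 to 337–364, then > 364: 3 + 12 + 1 = 16, plus a post-treatment category.
- Three severity grades (Protocol 5.1).
- A new record when severity or seriousness worsens (Protocol 5.2).

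**Step 1: direction.** The earliest record of a preferred term has, by definition, the smallest start day. Any other record chosen by severity starts on the same day or later. Literal application can therefore keep the onset or delay it, and cannot advance it.

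**Step 2: one hypothetical subject, one preferred term.** Mild and related on Day 5; moderate and not related on Day 40.

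| Selection | Onset interval |
|---|---|
| Earliest record | 1–7 |
| Severest record | 29–56 |

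If the second record fell on Day 150, the severest-record interval would be 141–168.

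**Step 3: when a worsening changes the interval.** The severest record is always the later one here, but the table changes only if a boundary is crossed. Within a 28-day interval, assume a start day equally likely to be any of the 28. A worsening *g* days later crosses with probability g/28 for g ≤ 28: 7/28 = 25% at one week, 14/28 = 50% at two weeks, and 100% at four weeks or more. Early intervals are narrower, so crossing is more likely there.

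**Step 4: separate repeats of the same preferred term.** The documents give no severity mix, so mild/moderate/severe mixes are assumed and occurrences are taken as independent. With grade probabilities p and cumulative probabilities F:
- two occurrences: P(severest is not first) = (1 − Σp²)/2, and P(tie) = Σp²;
- three occurrences: P(severest is not first) = 1 − Σ p·F².

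| Assumed mix (%) | Not first, 2 occurrences | Not first, 3 occurrences | Tie, 2 occurrences |
|---|---|---|---|
| 85/14/1 | 12.9% | 23.9% | 74.2% |
| 70/27/3 | 21.8% | 37.3% | 56.4% |
| 50/40/10 | 29.0% | 45.1% | 42.0% |

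For the first row, Σp² = 0.7225 + 0.0196 + 0.0001 = 0.7422, and (1 − 0.7422)/2 = 0.129. These shares apply only to subject-by-preferred-term pairs with repeats. They give the chance that a later record is selected, not that the interval changes. Ties are common and the SAP has no tie rule.

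**Step 5: tables that do not move.** Overall and ≥ 2% incidence count a subject once per preferred term whichever record is kept. The severity tables are served correctly by the rule.

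**Step 6: tables defined by an attribute.** In the Step 2 subject, selecting related records first gives a related count of 1. Picking the severest record first gives 0. Under that second order, with two occurrences and relatedness of probability r independent between them, the share of pairs with any related episode that is lost is (1 − r)/(2 − r): 0.2/1.2 = 17% at r = 0.8, 0.5/1.5 = 33% at r = 0.5, and 0.8/1.8 = 44% at r = 0.2. Independence overstates the loss. Selecting related records first, the loss is zero.

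**The case against.** The strongest reply is that the onset table carries its own, more specific instruction. SAP 10.2 names it by initial onset and Appendix 5 by time to first onset. A specific label normally overrides a general lead-in, and a careful programmer would use the first occurrence. This stands as evidence of intent. A reader might infer from the repeat rule that onset dates will in fact be shifted; the documents do not support that, because their own labels point the other way. The labels do not remove the contradiction, since the rule is stated without exception and nothing says the label prevails.

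A reader might also infer that every worsening AE is pushed later. That is too strong. Protocol 5.2 creates a new record for worsening in severity or in seriousness, and an AE that worsens only in seriousness leaves two records tied on severity. Even when the grade rises, the table changes only across an interval boundary.

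A third tempting inference is that drug-related events will be undercounted. The more natural reading of SAP 10.2 is that related TEAEs are selected first and then summarised; nothing is lost in that order. The same reading fits the serious, fatal and discontinuation tables. Loss needs the opposite order, which the SAP does not prescribe.

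Finally, the onset table is one descriptive summary among several, and listing AE-1 gives adverse events by subject, so the underlying information is not lost. That limits the consequence but does not correct a misallocated table.

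**Conclusion.** SAP 10.2 contains a real contradiction: a severest-record rule placed over a first-onset table. Applied literally to CT-8.8.1/8.8.2, it leaves a subject's onset interval unchanged or moves it later, never earlier. That direction follows from the definitions and needs no assumption.

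The frequency cannot be derived from the documents. Under the assumed severity mixes and independent repeats, a later record would be selected in 13% to 29% of subject-by-preferred-term pairs with two occurrences and in 24% to 45% with three, and only some of those would cross an interval boundary. For an AE that worsens in severity under Protocol 5.2, the later record is always the one selected.

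Overall and ≥ 2% incidence are unaffected. For the related, serious, fatal and discontinuation tables the finding is only that the order of selection is unstated.

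**What to change.** In SAP 10.2, limit the severest-event rule to the severity tables CT-8.3.1 and CT-8.3.2. For CT-8.8.1 and CT-8.8.2, state that onset is taken from the earliest qualifying treatment-emergent record of the preferred term. In CT-8.8.2, a qualifying record is one that is drug-related.

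As a clarification, add that the related, serious, fatal and discontinuation tables first select records with that attribute and then count each subject once per SOC and preferred term. If any table still needs one record chosen among equals, state the tie rule.

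The cost is one or two sentences for the correction and one more for the clarification. No new data are needed.
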